**Table 1-5: Schedule of Activities for Part A1 – Cohorts 1, 2, 4**

Assessments	Screening		Treatment				SFU Visit	Final Visit	
	-28 to -1	-14 to -1	Cycle 1 (28 days)		Cycle 2 (28 days)		Cycle 3 onwards (28 days)	Within 30 days after last dose	3 months after last dose
			1	15	1	15	1	15	
Cycle day									
Informed consent a	X								
Eligibility assessment b	X	X	X						
Demographic data and height	X								
Medical/surgical/cancer history/ concomitant disease and current medical status.	X		X						
ECG c	X		X		X		X	X	
Pregnancy test, if applicable d	X		X		X		X	X	X
UCB6114 - Cohort 1 (Q2W)			X	X	X	X	X	X	
UCB6114 – Cohort 2 (Q2W)			X	X	X	X	X	X	
UCB6114 – Cohort 4 (Q4W)				X		X			
Physical examination and weight e	X		X	X	X	X	X	X f	X
Vital signs (BP, HR, RR, and temperature) g	X		X	X	X	X	X	X f	X
ECOG performance status	X		X		X		X		X
Urinalysis h	X		X	X	X	X	X	X f	X
Hematology i	X		X	X	X	X	X	X f	X
Chemistry i	X		X	X	X	X	X	X f	X
Coagulation i	X		X		X		X		X

**Table 1-5: Schedule of Activities for Part A1 – Cohorts 1, 2, 4**

Assessments	Screening		Treatment				SFU Visit	Final Visit	
	-28 to -1	-14 to -1	Cycle 1 (28 days)		Cycle 2 (28 days)				
			1	15	1	15	1	15	
Cycle day									
Echocardiogram j	X						X	X	
Immunogenicity (ADA) l			X		X		X		
Tumor assessment m	X		Every 8 weeks from Day 1					X	
Concomitant medication	X		Recorded throughout					X	
Adverse Events (including DLT in Cycle 1) n	X		Recorded throughout					X	
Survival census								X	X
Biomarker analyses									
Blood collection for circulating gremlin-1 analysis o		X	X	X			X	X	
Blood collection for serum protein/proteomic analysis p		X		X	X		X	X	
Blood collection for transcriptomic analysis p		X		X	X		X	X	
Blood collection for genetic analysis		X							
Blood collection for ctDNA analysis		X		X	X		X	X	
Tumor biopsy for PD analysis q	X			X					
Historical tumor sample (from prior to entry into study) if available r	X								

ADA=anti-drug antibodies; AE=adverse event; BP=blood pressure; CT=computed tomography; ctDNA=circulating tumor DNA; h=hours; DLT=Dose limiting toxicity; ECG=electrocardiogram; ECOG=Eastern Cooperative Oncology Group; HR=heart rate; min=minutes; MRI=magnetic resonance imaging; PD=pharmacodynamic(s); PK=pharmacokinetic(s); Q2W=every 2 weeks; Q4W=every 4 weeks; RR= respiratory rate; SFU=Safety Follow Up;

Note: The allowed visit window is  $\pm$  2 days (unless specified otherwise). All assessments are to be performed prior to dosing with UCB6114 (unless specified otherwise)

a Informed consent must be given before any study-specific Screening procedures are performed.

b Eligibility must be confirmed prior to proceeding to tumor biopsy and on Cycle 1 Day 1 prior to dosing with UCB6114.

c ECGs are to be performed at screening; during Cycle 1 prior to dosing, at the end of the infusion, and 2h after the end of infusion; during each subsequent cycle prior to dosing with UCB6114 on Day 1. Electrocardiograms are to be performed in triplicate with the participant in a supine position after a minimum of 5min rest. When ECG coincides with PK (and PD), the ECG should be performed first.

d Serum pregnancy test must be performed at screening. Serum or urine pregnancy test must be performed prior to dosing on Day 1 of each cycle. Additional pregnancy tests should also be performed during the study if indicated.

e A complete physical examination is to be performed at Screening and on Cycle 1 Day 1 prior to dosing with UCB6114. Physical examination will be symptom-directed and performed prior to administration of UCB6114 on all other visits.

f Assessments to be performed on dosing day only. Not applicable for Cohort 4.

g On treatment days, vital signs will be assessed at multiple time points in a semi-supine position after 5min of rest; prior to dosing, 10min ( $\pm$ 5min) and 30min ( $\pm$ 10min) after the start of the infusion, at the end of the infusion (+15min) and 2h after the end of the infusion (+15min). In addition, on Cycle 1 Day 1, vital signs will also be assessed at 5h (+2h) after the end of the infusion. Vital signs will be assessed prior to collection of PK samples.

h If there are abnormalities in urine dipstick, a microscopic analysis should be performed (including crystals). Urinalysis does not have to be repeated on Cycle 1 Day 1 predose if performed within 72h of starting dosing.

i Laboratory tests (hematology, blood chemistry, and coagulation) do not have to be repeated on Day 1 predose if performed within 72h of starting dosing. They may be obtained 24h prior to the scheduled visit and may be obtained at local laboratories.

j During the treatment period, echocardiograms are to be completed at the beginning of Cycle 3 ( $\pm$  7 days), as clinically indicated afterwards, and at the SFU Visit.

 Immunogenicity (ADA) samples will be collected on Cycle 1 Day 1, Cycle 2 Day 1, Cycle 3 Day 1, and Day 1 of every third cycle thereafter (i.e. cycle 6, 9 etc.) and at the SFU Visit.

m Tumor assessments including spiral CT or MRI scan of the chest, abdomen, and any other area of known or suspected disease, must be obtained at Screening. A CT or MRI scan that is dated prior to consent (up to 42 days prior to starting IMP) for this study may be used as the Screening assessment, where this has been performed as per standard of care or at the end of a prior study. The same method of assessment is to be used per participant for the duration of study participation. Tumor assessments are to be performed every 8 weeks from Day 1 ( $\pm$  7 days). Tumor assessment at SFU is not required if the participant has withdrawn due to progressive disease or if the previous tumor assessment was within 42 days of SFU visit.

n Follow-up of AEs: AEs will be recorded up to 30 days after the last dose of study medication. After that time, any unresolved drug-related AEs should be followed until resolution or stabilization of the AE to obtain the date of resolution/stabilization (this follow-up can be via routine clinic visits or correspondence with a treating physician or other healthcare professional).

o Blood samples for circulating gremlin-1 analysis will be collected at Cycle 1 Day 1, pre-dose (within 30 min prior to dosing), end of infusion (+15min), and 4h (+1h) post-infusion as well as at Day 15 at predose (within 30min prior to dosing) or on day of visit if a non-dosing day. At all subsequent cycles, blood samples will be collected at Day 1 predose (within 30min prior to dosing) and at the SFU Visit; for Cycle 3 only, an additional 4h (+1h) postdose sample should be taken on Day 1. An additional sample should also be collected on the day of on-treatment biopsy (only if taking place on a day where no PK samples are scheduled).

p To be confirmed based on Part A Cohorts 1 to 3 analysis.

q Baseline biopsy should be collected between Day -28 and Day -1. Whenever possible, on-treatment biopsy should be performed within 2 weeks post Cycle 1 Day 15 (ie, between Cycle 1 Day 15 and Cycle 2 Day 1). If on-treatment biopsy occurs a non-dosing day, an additional PK and an additional cGremlin-1 samples should be collected on the day of biopsy.

r If an historical tumor biopsy specimen obtained prior to the participant's entry into the study (eg, at the time of diagnosis) is available, samples of this tissue will be requested for PD analysis at the time of consent.

**Table 1-6: Schedule of Activities for Part A1 – Cohort 3**

Assessments	Screening		Treatment				SFU Visit	Final Visit
	-28 to -1	-14 to -1	Cycle 1 (21 days)		Cycle 2 (21 days)			
Cycle day			1	15	1	15	1	15
Informed consent a	X							
Eligibility assessment b	X	X	X					
Demographic data and height	X							
Medical/surgical/cancer history/ concomitant disease and current medical status.	X		X					
ECG c	X		X		X		X	X
Pregnancy test, if applicable d	X		X		X		X	X
UCB6114 - Schedule 3 (Q3W)			X		X		X	
Physical examination and weight e	X		X		X		X	
Vital signs (BP, HR, RR, and temperature) f	X		X		X		X	
ECOG performance status	X		X		X		X	
Urinalysis g	X		X		X		X	
Hematology h	X		X		X		X	
Chemistry h	X		X		X		X	

**Table 1-6: Schedule of Activities for Part A1 – Cohort 3**

Assessments	Screening		Treatment				SFU Visit	Final Visit	
	-28 to -1	-14 to -1	Cycle 1 (21 days)		Cycle 2 (21 days)				
			1	15	1	15	1	15	
Cycle day									
Coagulation h	X		X		X		X		
Echocardiogram i	X					X		X	
Immunogenicity (ADA)			X		X		X k		
Tumor assessment l	X		Every 8 weeks from Day 1					X	
Concomitant medication	X		Recorded throughout					X	
Adverse Events (including DLT in Cycle 1) m	X		Recorded throughout					X	
Survival census								X	X
Biomarker studies									
Blood, collection for circulating gremlin-1 analysis n			X	X	X		X		
Blood collection for serum protein/proteomic analysis o		X			X		X		
Blood collection for transcriptomic analysis o		X			X		X		
Blood collection for genetic analysis		X							
Blood collection for ctDNA analysis		X			X		X		
Tumor biopsy for PD analysis p	X				X				
Historical tumor sample (from prior to entry into study) if available q	X								

ADA=anti-drug antibodies; AE=adverse event; BP=blood pressure; CT=computed tomography; ctDNA=circulating tumor DNA; h=hours; DLT=Dose limiting toxicity; ECG=electrocardiogram; ECOG=Eastern Cooperative Oncology Group; HR=heart rate; min=minutes; MRI=magnetic resonance imaging; PD=pharmacodynamic(s); PK=pharmacokinetic(s); Q3W=every 3 weeks; RR= respiratory rate; SFU=Safety Follow Up;

Note: The allowed visit window is  $\pm$  2 days (unless specified otherwise). All assessments are to be performed prior to dosing with UCB6114 (unless specified otherwise)

a Informed consent must be given before any study-specific Screening procedures are performed.

b Eligibility must be confirmed prior to proceeding to tumor biopsy and on Cycle 1 Day 1 prior to dosing with UCB6114.

c ECGs are to be performed at screening; during Cycle 1 prior to dosing, at the end of the infusion, and 2h after the end of infusion; during each subsequent cycle prior to dosing with UCB6114 on Day 1. Electrocardiograms are to be performed in triplicate with the participant in a supine position after a minimum of 5min rest. When ECG coincides with PK (and PD), the ECG should be performed first.

d Serum pregnancy test must be performed at screening. Serum or urine pregnancy test must be performed prior to dosing on Day 1 of each cycle. Additional pregnancy tests should also be performed during the study if indicated.

e A complete physical examination is to be performed at Screening and on Cycle 1 Day 1 prior to dosing with UCB6114. Physical examination will be symptom-directed and performed prior to administration of UCB6114 on all other visits.

f On treatment days, vital signs will be assessed at multiple time points in a semi-supine position after 5min of rest: prior to dosing, 10min ( $\pm$ 5min) and 30min ( $\pm$ 10min) after the start of the infusion, at the end of the infusion (+15min) and 2h after the end of the infusion (+15min). In addition, on Cycle 1 Day 1, vital signs will also be assessed at 5h (+2h) after the end of the infusion. Vital signs will be assessed prior to collection of PK samples.

g If there are abnormalities in urine dipstick, a microscopic analysis should be performed (including crystals). Urinalysis does not have to be repeated on Cycle 1 Day 1 predose if performed within 72h of starting dosing.

h Laboratory tests (hematology, blood chemistry, and coagulation) do not have to be repeated on Day 1 predose if performed within 72h of starting dosing. They may be obtained 24h prior to the scheduled visit and may be obtained at local laboratories.

i During the treatment period, echocardiograms are to be completed at the beginning of Cycle 3 ( $\pm$  7 days), as clinically indicated afterwards, and at the SFU Visit.

k Immunogenicity (ADA) samples will be collected on Cycle 1 Day 1, Cycle 2 Day 1, Cycle 3 Day 1, and Day 1 of every third cycle thereafter (i.e. cycle 6, 9 etc.) as well as at the SFU Visit.

l Tumor assessments including spiral CT or MRI scan of the chest, abdomen, and any other area of known or suspected disease, must be obtained at Screening. A CT or MRI scan that is dated prior to consent (up to 42 days prior to starting IMP) for this study may be used as the Screening assessment, where this has been performed as per standard of care or at the end of a prior study. The same method of assessment is to be used per participant for the duration of study participation. Tumor assessments are to be performed every 8 weeks from Day 1 ( $\pm$  7 days). Tumor assessment at SFU is not required if the participant has withdrawn due to progressive disease or if the previous tumor assessment was within 42 days of SFU Visit.

m Follow-up of AEs: AEs will be recorded up to 30 days after the last dose of study medication. After that time, any unresolved drug-related AEs should be followed until resolution or stabilization of the AE to obtain the date of resolution/stabilization (this follow-up can be via routine clinic visits or correspondence with a treating physician or other healthcare professional).

n Blood samples for circulating gremlin-1 analysis will be collected at Cycle 1 Day 1 at predose (within 30min prior to dosing), end of infusion (+15min), and 4h (+1h) post-infusion. An additional sample should be collected on Day 15 post-infusion on day of visit.. In all subsequent cycles blood samples will be collected

at Day 1 predose (within 30min prior to dosing) and at the SFU Visit; for Cycle 3 only an additional 4h (+1h) sample should be taken on Day 1. An additional sample should also be collected on the day of the on-treatment biopsy (only if taking place on a day where no PK samples are scheduled).

o To be confirmed based on Part A Cohort 1 to 3 analysis.

p Baseline biopsy should be collected between Day -28 and Day -1. Whenever possible, on-treatment biopsy should be performed within 2 weeks post Cycle 2 Day 1 (ie, between Cycle 2 Day 1 and Cycle 2 Day 15). If on-treatment biopsy occurs a non-dosing day, an additional PK and an additional cGremlin-1 samples should be collected on the day of biopsy.

q If an historical tumor biopsy specimen obtained prior to the participant's entry into the study (eg, at the time of diagnosis) is available, samples of this tissue will be requested for PD analysis at the time of consent.

The Schedule of Activities for Part B is provided in [Table 1-7](#).

**Table 1-7: Schedule of Activities for Part B**

Procedure	Screening		Treatment					SFU Visit	Final Visit	
	-28 to -1	-3 to -1	Cycle 1 & Cycle 2 (28 days)			Cycle 3 onwards (28 days)				
Cycle day			1	8	15	22	1	15	Within 30 days after final dose	3 months after final dose
Informed consent a	X									
Eligibility assessment b	X	X	X g							
Demographic data and height	X									
Medical/surgical/cancer history/concomitant disease and current medical status	X		X g							
ECG c	X	X	X		X		X		X	
Pregnancy test, if applicable d	X	X	X				X		X	X
TFD/TPI dispensing e		X	X							
TFD/TPI administration			TFD/TPI is administered orally twice daily on Days 1 to 5 and Days 8 to 12 of each cycle							
UCB6114 administration			UCB6114 is administered as an iv infusion on Days 1 and 15 of each cycle							
Physical examination and weight f	X	X	X	X g	X	X g	X	X		X
Vital signs (BP, HR, RR, and temperature) h	X	X	X	X g	X	X g	X	X		X
ECOG performance status h	X	X	X	X g	X	X g	X	X		X
Urinalysis i	X	X	X		X	X	X			X
Urinalysis for urinary markers of bone turnover			X		X		X			X
Hematology k	X	X	X	X	X	X	X	X		X
Blood chemistry l	X	X	X	X	X	X	X	X		X
Coagulation m	X	X	X		X g		X			X

**Table 1-7: Schedule of Activities for Part B**

Procedure	Screening		Treatment						SFU Visit	Final Visit
	-28 to -1	-3 to -1	Cycle 1 & Cycle 2 (28 days)			Cycle 3 onwards (28 days)				
Cycle day	1	8	15	22	1	15				
Blood collection for serum markers of bone turnover			X		X		X		X	
Blood collection for immunogenicity (ADA)			X				X p		X	
Blood collection for circulating gremlin-1 analysis	X	X o	X o,q		X q		X p,q		X	
Blood collection for genetic analysis	X	X o								
Blood collection for ctDNA analysis	X	X o	X o		X		X		X	
Echocardiogram	X						X u		X	
Tumor assessments r	X		Every 8 weeks from Day 1						X	
Historical tumor sample if available s	X									
Concomitant medication	X		Recorded throughout						X	
Adverse events t	X		Recorded throughout						X	
Survival census									X	X

ADA=antidrug antibody; AE=adverse event; ALP=alkaline phosphatase; BP=blood pressure; CT=computed tomography; ctDNA=circulating tumor DNA; DLT=dose-limiting toxicity; ECG=electrocardiogram; ECOG=Eastern Cooperative Oncology Group; h=hour(s); HR=heart rate; iv=intravenous; min=minute(s); MRI=magnetic resonance imaging; PD=pharmacodynamic(s); PK=pharmacokinetic(s); RR=respiratory rate; TFD/TPI= trifluridine/tipiracil; SFU=Safety Follow-Up

Note: The allowed visit window is  $\pm 2$  days (unless specified otherwise). All assessments are to be performed prior to dosing with IMP (unless specified otherwise).

a Informed consent must be given before any study-specific Screening procedures are performed.

b Eligibility must be confirmed within 3 days prior to starting any IMP. Confirmation does not have to be repeated on Day 1 predose if it was performed within 3 days prior to starting any IMP.

c ECGs are to be performed prior to dosing with IMP in triplicate with the participant in a supine position after a minimum of 5 minutes of rest. ECGs are to be performed in Screening and do not have to be repeated on Day 1 predose if performed within 3 days prior to starting any IMP. On Days 1 and 15 of Cycle 1 only, ECGs will also be performed at multiple timepoints in relation to dosing with UCB6114 (pre-infusion, end of infusion, and at 2 hours post infusion). When ECG coincides with blood collection for PK (and PD), the ECG should be performed first.

d Serum pregnancy test must be performed in Screening and does not have to be repeated on Day 1 predose if performed within 3 days prior to starting any IMP. If a serum pregnancy test was performed at Screening more than 3 days prior to starting any IMP, a urinary pregnancy test can be performed on Day 1 prior to dosing with any IMP. A serum or urinary test can be performed on all other visits.

e TFD/TPI can be dispensed once eligibility is confirmed (see footnote b).

**Table 1-7: Schedule of Activities for Part B**

Procedure	Screening		Treatment						SFU Visit Within 30 days after final dose	Final Visit 3 months after final dose
	-28 to -1	-3 to -1	Cycle 1 & Cycle 2 (28 days)			Cycle 3 onwards (28 days)				
Cycle day	1	8	15	22	1	15				

f A complete physical examination is to be performed in Screening and does not have to be repeated on Day 1 pre-dose if performed within 3 days prior to starting any IMP. Physical examinations will be symptom-directed and performed prior to administration of IMP on all other visits.

g Not to be done in Cycle 2.

h Vital signs and ECOG performance status are to be performed in Screening and do not have to be repeated on Day 1 pre-dose if performed within 3 days prior to starting any IMP. Vital signs on treatment days with UCB6114 will be assessed at multiple time points in a semi-supine position after 5min of rest: pre-dose, 10min ( $\pm$ 5min) and 30min ( $\pm$ 10min) after the start of the infusion, at the end of the infusion (+15min); and at 1h (+15min) after the end of the infusion. In addition, on Cycle 1 Day 1 vital signs will be assessed at 2h (+1h) and 5h (+1h) after the end of the infusion.

i Urinalysis is to be performed in Screening and does not have to be repeated on Day 1 pre-dose if performed within 3 days prior to starting any IMP. If there are abnormalities in urine dipstick, a microscopic analysis should be performed (including crystals).

j Deleted

k Hematology is to be performed in Screening and does not have to be repeated on Day 1 pre-dose if performed within 3 days prior to starting any IMP. At all other visits, the hematology sample may be obtained 24h prior to the scheduled visit.

l Blood chemistry is to be performed in Screening and does not have to be repeated on Day 1 if performed within 3 days prior to dosing with any IMP. At all other visits blood, the chemistry sample may be obtained 24h prior to the scheduled visit. In the case of liver function abnormalities considered potential Hy's law cases, the liver-specific ALP must be separated from the total in participants with bone metastases and used to assess the liver function instead of the total ALP.

m Coagulation is to be performed in Screening and does not have to be repeated on Day 1 pre-dose if performed within 3 days prior to starting any IMP. At all

o No sample required if done previously.

p To be completed in Cycle 3 and thereafter in even cycles only (i.e., Cycle 4, 6)

q Sample for circulating gremlin-1 will be collected at the same time as PK samples (ie, 30 minutes prior to dosing with UCB6114).

r Tumor assessments including spiral CT or MRI scan of the chest, abdomen, pelvis, and any other areas of known or suspected disease, must be obtained at Screening. A CT or MRI scan that is dated prior to consent (up to 42 days prior to starting IMP) for this study may be used as the Screening assessment, where this has been performed as per standard care or at the end of a prior research study. The same method of assessment is to be used per participant for the duration of study participation. Tumor assessments are to be performed every 8 weeks from Day 1 ( $\pm$ 7 days). Tumor assessment at SFU is not required if the participant has withdrawn due to progressive disease or if the previous tumor assessment was within 42 days of SFU visit.

s If an historical tumor biopsy specimen obtained prior to the participant's entry into the study (eg, at the time of diagnosis) is available, samples of this tissue will be requested for PD analysis.

t Including DLT in Cycle 1. Follow-up of AEs: AEs will be recorded up to 30 days after the final dose of IMP. After that time, any unresolved drug-related AEs should be followed until resolution or stabilization of the AE to obtain the date of resolution/stabilization (this follow-up can be via routine clinic visits or correspondence with a treating physician or other healthcare professional).

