### **9.8 Pharmacodynamics**

Planned time points for all tertiary/exploratory PD assessments are provided in the Schedules of Activities for Part A (Table 1-4), Part A1 (Table 1-5 and Table 1-6), Part B (Table 1-7), and Part C (Table 1-8). All tertiary/exploratory PD assessments for Parts D, E, F, and G will be defined in a protocol amendment.

Blood samples for PD analysis will be collected at the time points discussed in the following sections.

Blood samples of various volumes may be collected for analysis in a range of PD assays ([Table 9-1](#)). In Part A, the number of blood samples and total volume collected per cycle and at the SFU Visit will be as follows:

- In Cycle 1, up to 12 blood samples totaling approximately 83.5mL
- In Cycle 2, up to 5 blood samples totaling approximately 35.5mL
- In Cycle 3, up to 5 blood samples totaling approximately 35.5mL
- In Cycle 4, up to 4 blood samples totaling approximately 15.5mL
- At the SFU Visit, up to 5 blood samples totaling approximately 35.5mL

In Part A1, the number of blood samples and total volume collected per cycle and at the SFU Visit will be as follows:

- In Screening, up to 4 blood samples totaling approximately 36 mL in each Cohort
- Cycle 1, up to 7 blood samples totaling approximately 43.5mL in Cohorts 1, 2, 4 and up to 4 blood samples totaling approximately 16mL in Cohort 3
- In Cycle 2, up to 4 blood samples totaling approximately 31.5mL in each Cohort
- In Cycle 3 up to 5 blood samples totaling approximately 35.5mL in each Cohort
- From Cycle 4 onwards and at the SFU Visit up to 4 blood samples totaling approximately 31.5mL in each Cohort

One additional sample for circulating gremlin-1 (4mL) may be taken on the day of the on-treatment biopsy if taking place on a day where no circulating gremlin-1 sample is scheduled.

In Parts B and C, the number of blood samples and total volume collected per cycle and at the SFU Visit will be as follows:

- In Screening, up to 3 blood samples totaling approximately 32.5mL
- In Cycle 1, up to 4 blood samples totaling approximately 32mL
- In Cycle 2, up to 6 blood samples totaling approximately 56mL
- From Cycle 3 onwards, up to 3 blood samples totaling approximately 28mL
- At the SFU Visit, up to 3 blood samples totaling approximately 28mL

Tumor biopsies will also be collected during the study (see Section [9.8.7](#)).

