**Table 9-9: Sample time points for serum gremlin-1 analysis in Part B and Part C**

Cycle	Day	Sampling time relative to dosing with UCB6114	Sampling time
Screening	Once between Day -28 and -1	NA	NA
Cycle 1	Day 15	Within 0.5h prior to dosing	Predose
Cycle 2	Day 1	Within 0.5h prior to dosing	Predose
	Day 15	Within 0.5h prior to dosing	Predose
Cycle 3 (onward) a	Day 1	Within 0.5h prior to dosing	Predose
SFU Visit	On day of visit	On day of visit	NA

h=hour; NA=not applicable; SFU=Safety Follow-Up

a To be completed in cycle 3 and thereafter in even cycles only (ie, Cycle 4, 6)**9.8.2 Blood samples for serum protein analysis and blood transcriptomics**

In Part A and Part A1, whole blood samples of approximately 5mL per time point will be collected and processed to serum for analysis of protein markers. An additional whole blood sample of 2.5mL per time point may also be collected for potential transcriptomic analysis. Samples for analysis of protein markers or potential transcriptomic analysis will not be obtained in Part B or Part C.

Sampling time points for these assays are detailed in [Table 9-10](#) (Part A) and [Table 9-11](#) (Part A1).

Instructions pertaining to sample collection, processing, storage, labeling, and shipping are provided in the laboratory manual for this study.

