**Table 9-14: Sample time points for ctDNA analysis in Part B and Part C**

Cycle	Day	Sampling time relative to dosing with UCB6114	Sampling time
Screening	Once between Day -28 and -1	NA	NA
Cycle 1	Day 15	Within 0.5h prior to dosing	Predose
Cycle 2	Day 1	Within 0.5h prior to dosing	Predose
	Day 15	Within 0.5h prior to dosing	Predose
Cycle 3 (onward)	Day 1	Within 0.5h prior to dosing	Predose
SFU Visit	On day of visit	On day of visit	NA

ctDNA=circulating tumor DNA; h=hour; NA=not applicable; SFU=Safety Follow-Up

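### Footnote o in Tables 1-7 and 1-8 has no cycle limit and, read literally, waives the Cycle 2 Day 1 gremlin-1 and ctDNA samples listed in Section 9.8

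*Protocol*

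**What the plan says.** Tables 1-7 (Part B) and 1-8 (Part C) put the first two cycles under one header, "Cycle 1 & Cycle 2 (28 days"), with a single set of Day 1, 8, 15 and 22 columns. In both tables the shared Day 1 cell for circulating gremlin-1 carries footnotes o and q, and the shared Day 1 cell for ctDNA carries footnote o. Footnote o reads "No sample required if done previously". Footnote q only fixes the timing of a gremlin-1 sample relative to dosing. The Day 15 cells do not carry footnote o. It does appear on the second Screening column for gremlin-1, ctDNA and genetic analysis.

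The same tables have another marker for separating the two cycles, footnote g: "Not to be done in Cycle 2". It is not used on the gremlin-1 or ctDNA cells.

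Table 9-9 (gremlin-1) and Table 9-14 (ctDNA) each list one Screening sample, Cycle 1 Day 15, Cycle 2 Day 1, Cycle 2 Day 15, Day 1 from Cycle 3 onward, and the SFU Visit. For Cycle 2 Day 1 the stated time is "Within 0.5h prior to dosing". Neither table has a Cycle 1 Day 1 sample, and neither carries an exception matching footnote o. For Parts B and C, Section 9.8 states: "In Cycle 2, up to 6 blood samples totaling approximately 56mL".

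**The concern.** At Cycle 2 Day 1 the literal condition of footnote o is met for any participant sampled on schedule, since the Screening and Cycle 1 Day 15 samples come earlier. The schedule of activities then releases the site from a draw that Section 9.8 lists separately. The two parts of the protocol give different instructions for the same visit.

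A predose sample that is not drawn cannot be recovered. Change in protein markers and in ctDNA by scheduled assessment and dose level is a tertiary/exploratory endpoint of Parts B and C (Table 3-2). If some sites read the footnote as a baseline fallback and others as a general waiver, data would be unevenly missing at one nominal time point for a reason unrelated to the participants.

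**Working it through.** The protocol's blood counts show which reading of footnote o agrees with the rest of the text.

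**Inputs.** Gremlin-1 is 4 mL per sample (Section 9.8.1), ctDNA 20 mL (9.8.3), serum bone markers 4 mL (9.8.4) and genetic analysis 8.5 mL (9.8.6). Time points come from Tables 9-9, 9-14 and 9-16. Stated totals are those in Section 9.8 for Parts B and C.

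**Reproducing the stated totals.**
- Screening: gremlin-1 4 + ctDNA 20 + genetic 8.5 = 32.5 mL, 3 samples. Stated: 3 and 32.5 mL.
- Cycle 1: Day 1 bone markers 4; Day 15 bone markers 4 + gremlin-1 4 + ctDNA 20. Total 32 mL, 4 samples. Stated: 4 and 32 mL.
- Cycle 2: 4 + 4 + 20 on Day 1 and again on Day 15 = 2 × 28 = 56 mL, 6 samples. Stated: 6 and 56 mL.
- Cycle 3 onward: 4 + 4 + 20 = 28 mL, 3 samples. Stated: 3 and 28 mL.

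All four totals match.

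**Applying footnote o to the shared Day 1 cell.**
- At Cycle 1 Day 1, waiving gremlin-1 and ctDNA gives the stated 4 samples and 32 mL. Drawing them would give 6 samples and 32 + 24 = 56 mL, which does not match. The footnote fits here.
- At Cycle 2 Day 1, waiving them gives 6 − 2 = 4 samples and 56 − (4 + 20) = 32 mL, against the stated 6 and 56 mL. The footnote does not fit here.

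The footnote is therefore consistent with Section 9.8 only as a fallback for a baseline sample missed at Screening.

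**Effect on the sampling sequence.** With 28-day cycles, Cycle 2 Day 1 is Day 29 and Cycle 2 Day 15 is Day 43. Values are planned at Days 15, 29 and 43, a spacing of 14 days. Without Day 29 the interval is 43 − 15 = 28 days. A participant who stops after Cycle 2 Day 1 but before Cycle 2 Day 15 would have one on-treatment value (Day 15) before the SFU Visit instead of two.

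**Ceiling on samples lost.** Up to 27 participants in each part gives 2 × 27 = 54. One gremlin-1 and one ctDNA sample each gives 54 × 2 = 108.

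**The case against.** The strongest reply is that the intended design is clear and the footnote is only loosely worded. It waives a draw and does not prohibit one. Its use on the second Screening column and on the genetic row, a one-time sample, suggests that done previously means the baseline sample has already been obtained. Several neighbouring Part B footnotes also refer to Day 1 predose without naming Cycle 1 and clearly concern the start of treatment. The Day 1 cells carry an X without footnote g, so by the table's own convention they are active in Cycle 2. Sections 9.8.1 and 9.8.3 refer the reader to Tables 9-9 and 9-14, which are explicit.

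Most of this stands as evidence of intent, and a careful site may well read it that way. It does not remove the conflict. An X without footnote g does not override a waiver attached to the same cell, and the waiver's literal condition is already met by Cycle 2 Day 1 for a participant sampled on schedule. The Section 9.8 totals are stated as upper limits, so they support the intended reading but do not by themselves compel the draw.

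Stronger readings are tempting but unsupported. A reader might infer that sites are instructed to omit the samples; the words only make them not required. A reader might also infer that dose decisions are compromised, because Sections 4.1.4.3 and 4.1.5.3 include PD biomarkers among the considerations for the recommended Phase 2 dose. The documents attach no decision rule to the Cycle 2 Day 1 value, and the mTPI tables work on DLT counts alone.

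**Conclusion.** Footnote o is wrong as written in both tables, in a limited way. Read literally, it waives the Cycle 2 Day 1 gremlin-1 and ctDNA samples, in conflict with Tables 9-9 and 9-14 and with the Cycle 2 count in Section 9.8. Where the waiver is used, the loss is one gremlin-1 and one ctDNA sample (24 mL of the planned 56 mL) per participant reaching Cycle 2, and the interval without a value lengthens from 14 to 28 days.

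The figure of 108 samples is a ceiling, not an estimate. It assumes that both parts enrol 27, that every participant reaches Cycle 2 Day 1, and that the samples are waived every time. Only tertiary/exploratory PD endpoints are affected. Primary safety and secondary PK endpoints, and the Day 15 samples, are not.

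**What to change.** In Tables 1-7 and 1-8, limit footnote o to the baseline sample, meaning the second Screening column and Cycle 1 Day 1. Add that the Cycle 2 Day 1 gremlin-1 and ctDNA samples are taken predose as in Tables 9-9 and 9-14.

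The cost is one footnote in two tables. The visit already takes place, bone-marker blood is already drawn at it, and the 24 mL is already counted in Section 9.8, so participants have no burden beyond what the protocol already states.
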